Research proposal

1. Project title

The effects of different inspiratory pressures on the diaphragmatic thickness fraction and sternocleidomastoid muscle activation in people after stroke

2. Abstract

This study is a cross-sectional study to determine the optimal inspiratory muscle training (IMT) intensity for stroke survivors. Participants will breathe through a pressure threshold inspiratory loading device with varying loads in random order. During the test, accessory inspiratory muscle (sternocleidomastoid muscles) activity will be measured with surface electromyography (sEMG) and diaphragm thickness will be used to assessed with ultrasonography. Repeated-measures ANOVA will be used for statistical analysis to determine the most effective training intensity.

3. Project objectives

Introduction:

Stroke was the second largest cause of global death and disability in 2019 [1]. Direct medical costs for stroke in China was 50 billion yuan (nearly 7.69 billion US dollars) in 2015, and this accounted for the highest medical cost in China [2]. In 2016, the Global Burden of Disease (GBD) study estimated that the lifetime risk of stroke from the age of 25 years was 39.3% in China, which is the highest estimated risk in the world [3]. In 2018, stroke was the third highest disease cause of death, accounting for 1.57 million deaths in China [4].

Stroke not only causes impairment of motor function but can also affect lung function [5]. The lung function (e.g. forced vital capacity (FVC), forced expiratory volume in one second (FEV1), maximal inspiratory pressure (MIP), peak expiratory flow (PEF)) in people after stroke was reported significantly lower than the age and gender-matched healthy adults [6, 7]. Impaired lung function in people after stroke not only leads to high risk of pneumonia, poor functional outcomes and prolonged hospitalization but may also increase mortality [8-10].

Diaphragmatic weakness is considered to be the major reason contributing to the reduction of lung function of people after stroke [11]. Diaphragm, as the primary inspiratory muscle, accounts for approximately 75% of the airflow into the lungs during quiet breathing [12]. However, most people after stroke have diaphragmatic weakness due to the loss of central motor control, leading to paralysis of the diaphragm in the contralateral side [13, 14]. Diaphragmatic weakness can lead to asymmetric respiratory chest movements, changes in the respiratory mechanism, and consequently reduced lung function [11, 14, 15]. The thickness of the affected diaphragm of patients after subacute and chronic stroke was found only to have nearly 50% of those of healthy individuals [13]. Contraction of diaphragm fibers can be quantified by the diaphragmic thickening fraction (DTF), determined by “(thickness of the diaphragm at end inspiratory - thickness at end expiratory)/thickness at end expiratory” [16]. A reduction in diaphragmatic contraction was reported to be significantly correlated with decreased lung function (e.g. FVC, FEV1, MIP, PEF) in people after stroke [13, 17].

Inspiratory muscle training (IMT) is an intervention designed for improvement of inspiratory muscle (including the diaphragm) strength and endurance in healthy adults and patients suffering from different diseases (e.g. Parkinson, chronic obstructive pulmonary disease, cardiovascular disease) [18-21]. Regarding the IMT training protocol, the commonly reported training intensities varied between 30-80% of MIP in people after stroke [22-24]. Although the diaphragm is the primary inspiratory muscle, the use of IMT may not help improve the diaphragmatic contraction under some circumstances. Previous studies suggested that, in healthy adults and people receiving mechanical ventilation, when inspiratory load exceeds the capacity of the diaphragm (higher than 60% MIP), the accessory respiratory muscle (in particular the sternocleidomastoid muscle) would be activated dramatically, which would increase work of breathing and fatigue [25, 26]. Other studies also reported that high IMT intensity may have the risk to increase the work of breathing thereby leading to fatigue [27] or resulting in a decrease, rather than increase, in surface electromyography signals in diaphragmatic activity [27]. It is postulated that IMT recruits accessory muscles such as sternocleidomastoid rather than diaphragm during the practice [24]. Hence, evaluation of effectiveness of IMT on DTF in people after stroke and further investigation on determining an optimal training protocol including inspiratory effort and training intensity for recruiting diaphragmatic activities in the stroke population are warranted.

Aims of the study:

To determine the optimal training intensity that is associated with the strongest diaphragmic thickening fraction in people after stroke.

Project significance:

Outcomes of this project study will fill the existing knowledge gaps in the understanding of the relationship between inspiratory pressure and recruitment of diaphragmatic muscles in people after sub-acute and chronic stroke.

4. Research methodology

Study design:

This study will be a cross-sectional study.

Participants:

Individuals who have had a stroke and healthy adults will be invited to participate in this study.

Participants recruitment for people after stroke:

The inclusion criteria are: (1) age \geq 18 years; (2) clinically diagnosed with ischemic and/or hemorrhagic stroke; (3) duration of stroke range from 1 month to 12 months after diagnosis; (4) had no facial palsy, which could prevent proper labial occlusion; (5) had not undergone thoracic or abdominal surgery; (6) could understand and follow the verbal instruction; (7) stable cardiac conditions; (8) no previous history of respiratory problems.

The exclusion criteria are: (1) acute myocardial infarction or acute heart failure; (2) acute pain on chest or abdominal; (3) with the clinical signs of significant pulmonary disease; (4) consciousness impaired; (5) patient with nasal feeding tube, tracheal tube and/or any condition, which prevent the measurement or training.

Recruitment of healthy participants:

The inclusion criteria are: (1) age ≥ 18 years; (2) had not undergone thoracic or abdominal surgery; (3) no previous history of respiratory problems.

The exclusion criteria are: (1) acute myocardial infarction or acute heart failure; (2) acute pain in the chest or abdominal; (3) with the clinical signs of significant pulmonary disease; (4) unstable hypertension, arrhythmias, or unstable cardiovascular conditions, such as fluctuations in blood pressure and heart rate, indicate poor cardiac prognosis or the need for vasopressor medications; (5) pregnant.

Ethical approval:

Ethical approval will be sought from the Research Ethics Committee of Hong Kong Metropolitan University and Shenzhen Second People's Hospital.

Sample size calculation:

Sample size calculation will be based on the use of repeated-measures analysis of variance (ANOVA) using the G*Power 3.1. Considering an effect size of 0.2, an alpha error probability of 0.05 and a power of 0.80, the estimated sample size is 54 participants. An additional 20% of the sample size will be included to account for attrition. The final estimated sample size will be at least 130 participants (65 for each cohort).

Procedure:

The nature of the study will be explained to the participants and written informed consent will be obtained. Demographic data of each participant including age, sex, height, weight, BMI, percent body fat, lean body mass, and smoking history will be recorded. For people after stroke, the stroke type (cerebral infarction, intracerebral hemorrhage), medical history (hypertension, diabetes mellitus, cardiovascular disease, lipidemia, kidney disease) will also be recorded. The National Institutes of Health Stroke Scale (NIHSS), Modified Rivermead Mobility Index (MRMI), Modified Rankin Scale (mRS), Barthel index (BI) will be retrieved from the patient's medical record.

Participants will be invited to attend the cardiopulmonary laboratory of the hospital at a time > 2 hours after a light meal. Participants are requested to avoid caffeine-containing products, nicotine, alcohol and vigorous exercise for at least 12 hours before attending the laboratory.

Each participant will be asked to perform the lung function test to measure the FVC, FEV₁, and MIP after including the study. After completing the baseline lung function test, participant will be required to sit on the chair and rest for 15 minutes, after that, two trained researchers will use two identical ultrasonography to measure the left and right diaphragmatic thickness simultaneously at quiet breathing, the end of tidal inspiratory and the end of tidal expiratory, respectively. 3 ultrasonic images will be captured to calculate the mean diaphragmatic thickness of each breathing status. In order to determine the inter-rater reliability of the measurement of ultrasonography of

those two trained researchers, 20 participants will be chosen out randomly to receive twice diaphragmatic thickness measurement at quiet breathing, the end of tidal inspiratory and the end of tidal expiratory. However, during the second measurement, those two trained researchers will change their position to measure the contralateral side diaphragmatic thickness independently.

After the baseline measurement, all participants will be requested to use a nose clip to hold the nose and breathe with the mouth through a pressure threshold inspiratory loading device (POWERbreathe, KH2, England). The inspiratory pressure will be set at 30%, 40%, 50%, 60%, 70%, or 80% of their MIP, in random order. Each MIP intensity protocol consists of 10 breaths. The procedure of IMT is followed by the published research protocols in people after stroke [28]. All MIP intensity protocols will be conducted in one day. A period of at least 10 minutes of rest time will be allowed between different protocols of contraction intensity (% MIP) on the same day [29].

Thickness of the left and right diaphragm (stroke and non-stroke), will be measured simultaneously by two identical ultrasonography at the end of maximum inspiration of 10 breaths of each MIP intensity protocol. The diaphragm thickness of both the left and right diaphragm at the end inspiratory breaths of the 10 breaths of each MIP intensity protocol will be recorded. Surface electromyography (sEMG) will be used to measure the activity of accessory muscle (sternocleidomastoid muscles) during each MIP intensity protocol. The % of MIP that associates with the highest calculated DTF and a relatively stable change in the activity of accessory muscles will be considered an appropriate training intensity for further IMT protocols.

The self-perceived exertion level will also be determined by the Rate of Perceived Exertion Borg scale at the end of each MIP intensity protocol [30].

All research procedures will be repeated again after 2 days to examine the test-retest reliability of ultrasonographic measurements of DTF.

Outcome measures:

[figure not shown]
Lung function

FVC, FEV1 will be measured by using a spirometer (XEEK, X1, China), MIP will be measured by another device (Power Breathe, KH2, England). During the lung function tests, participants need to remain in the upright sitting position with a nose clip that tightly fits the nostrils. To record MIP, participants will be instructed to perform inspirations against an obstructed airway within the mouthpiece at near-residual volume. All lung function tests require each participant to inhale and exhale as hard and as fast as possible, then complete the cycle by inspiring as hard and rapidly as possible. Each test will be required to be performed at least three times, with each test not differing by more than 5% or 100 milliliters. The largest value obtained from the three executions will be used in the final analysis [31]. All tests will follow the recommendations proposed by the guidelines of the lung function tests [32].

Power Breathe (KH2)

The Power Breathe KH2 is an inspiratory muscle training device designed to improve the strength and endurance of inspiratory muscles (as shown in picture 1) [33]. It consists of a mouthpiece and a breathing valve. The valve is calibrated to provide a specific resistance during inhalation. The resistance can be adjusted on the device according to the IMT prescription. Participant needs to inhale through the mouthpiece

and drive their inspiratory muscle to contract against the external inspiratory breathing load.

- (a) the lateral side of Power Breathe (KH2).
- (b) the front side of Power Breathe (KH2).
- (c) the back side of Power Breathe (KH2), the top part (blue color) is the breathing valve.

Muscle activity of sternocleidomastoid muscles

Surface electromyography (sEMG) (Telemyo 900 from Noraxon USA) will be used to measure accessory inspiratory muscle (sternocleidomastoid muscles) activity during each MIP intensity protocol. The electrodes for sEMG will be attached to the bilateral sternocleidomastoid muscles (SCM). The locations of the electrodes will be placed at the mid-point of the left and right SCM muscles to measure the muscle activity of IM (shown in figure 1(a)). The sEMG responses will be amplified (gain $\times 1,000$); the band-pass will be filtered between 5 and 500 Hz, and digitized at a sampling rate of 1 kHz by using an analogue to-digital converter. The acquired data will be later analyzed using matching software.

The measurement of diaphragmatic thickness

Diaphragmatic thickness will be measured by the ultrasound machine (Mindray 9, Shenzhen, PRC). Ultrasonography is a portable, noninvasive emerging technique allowing easy and rapid estimation of muscle thickness [34, 35]. It not only can avoid the risk of exposure to radiation in medical facilities but also the reliability in providing a clear visualization of the muscle morphology at the zone of apposition [35, 36].

For consistency, all measurements will be conducted using the same transducer probe (model SuperLinear SL18-8; SuperSonic Imagine) with a bandwidth of 5 -18Hz of B mode. Ultrasonography will be performed by two trained physiotherapist who operates the machine under the guidance of a radiologist who is trained to use diagnostic ultrasound.

[figure not shown]
Participant needs to remain in the upright sitting position on the chair during the measurement procedure. To measure the right diaphragmatic thickness, the transducer probe will be placed in the right intercostal space above the eighth or ninth intercostal space, between the antero-axillary and mid-axillary lines with a 45° angle tilt between

the surface of the abdominal wall in the cephalic direction, where the diaphragm is most suitable visualized (shown in figure 1(a)). To measure the left diaphragmatic thickness, the transducer will be placed in the left intercostal space above the eighth or ninth intercostal space, between the anterior subcostal region between the anterior and midaxillary lines (shown in figure 2(a)). The diaphragm is observed as a three-layered structure, with the hypoechogenic muscular layer bordered by echogenic layers—the peritoneum and the diaphragmatic pleurae (as shown in figure 2(b) and figure 2(c)).

[figure not shown]
Figure 1 The placement of transducer probes, surface electromyography electrodes and image of the diaphragm

(a) The placement of transducer probes when measure of the right and left diaphragm by ultrasonography in people after stroke (left hemiplegia); The blue points represent the locations of surface electromyography electrodes on the sternocleidomastoid muscles.

[figure not shown]

(b) Diaphragmatic thickness images of the left diaphragm (stroke side) at the end of tidal expiration and the end of maximum inspiration at 30 %MIP.

(c) Diaphragmatic thickness images of the right diaphragm (non-stroke side) at the end of tidal expiration and the end of maximum inspiration at 30 %MIP.

Research flow chart

Reporting of adverse event:

Though various measures will be taken to minimize the risk of adverse event throughout the study, any adverse events that might happen will be recorded.

Statistical analysis:

All data will be reported as mean \pm standard deviation (SD) unless otherwise indicated. Demographic data and clinical characteristics for all participants will be summarized using descriptive statistics. Repeated-measures ANOVA will be used to compare the differences of DTF and sEMG parameters determined at each inspiratory pressure separately. Intraclass correlation coefficient will be used to determine the inter-rater reliability of two ultrasonic operators and examine the test-retest reliability coefficient of ultrasonographic measurements of DTF recorded with different inspiratory pressures.

P value will be set at 0.05. All data will be analyzed using the IBM SPSS Statistics for Windows, Version 25.0 (Armonk, NY: IBM Corp).

References:

1. Gbd, S., Global, regional, and national burden of stroke and its risk factors, 1990-2019: a systematic analysis for the Global Burden of Disease Study 2019. *Lancet Neurol*, 2021. 20(10): p. 795-820.
2. Wu, X., et al., The hospital costs of stroke patients in Chinese island populations: an 11-year tendency analysis. *J Stroke Cerebrovasc Dis*, 2015. 24(5): p. 988-992.
3. Feigin, V., et al., Global, Regional, and Country-Specific Lifetime Risks of Stroke, 1990 and 2016. *N Engl J Med*, 2018. 379(25): p. 2429-2437.
4. Li X and Z. X., Annual data set on national mortality surveillance 2018. Beijing: China Science and Technology Press, 2019.
5. Menezes, K.K., et al., Respiratory muscle training increases respiratory muscle strength and reduces respiratory complications after stroke: a systematic review. *J PHYSIOTHER*, 2016. 62(3): p. 138-44.
6. Liu, X., et al., Assessment of Diaphragm in Hemiplegic Patients after Stroke with Ultrasound and Its Correlation of Extremity Motor and Balance Function. *Brain Sciences*, 2022. 12(7): p. 882.
7. Lista-Paz, A., et al., Pulmonary function in patients with chronic stroke compared with a control group of healthy people matched by age and sex. *Physiother Theory Pract*, 2022: p. 1-9.
8. Wilson, R., Mortality and cost of pneumonia after stroke for different risk groups. *J Stroke Cerebrovasc Dis*, 2012. 21(1): p. 61-67.
9. Saposnik, G., et al., Variables associated with 7-day, 30-day, and 1-year fatality after ischemic stroke. *Stroke*, 2008. 39(8): p. 2318-2324.

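### The planned repeated-measures ANOVA cannot show which load gives the strongest DTF, and no load-to-load comparison, interval or multiplicity rule is planned to do so

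*Combined protocol and SAP*

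**What the plan says.** The document is the combined protocol and SAP.

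- **Aims of the study** (section 3): "To determine the optimal training intensity that is associated with the strongest diaphragmic thickening fraction in people after stroke".
- **Abstract** (section 2): "Repeated-measures ANOVA will be used for statistical analysis to determine the most effective training intensity".
- **Sample size calculation** (section 4): "Sample size calculation will be based on the use of repeated-measures analysis of variance (ANOVA) using the G*Power 3.1". It continues: "Considering an effect size of 0.2, an alpha error probability of 0.05 and a power of 0.80, the estimated sample size is 54 participants". A 20% allowance then gives 65 per cohort and 130 in total.
- **Procedure** (section 4): six loads from 30% to 80% of MIP in random order, with DTF recorded on the left and right (stroke and non-stroke) sides. The load considered appropriate for later training protocols is "The % of MIP that associates with the highest calculated DTF and a relatively stable change in the activity of accessory muscles".
- **Statistical analysis** (section 4): "Repeated-measures ANOVA will be used to compare the differences of DTF and sEMG parameters determined at each inspiratory pressure separately". Data are summarised as mean and "standard deviation (SD) unless otherwise indicated", intraclass correlations cover reliability, and P is set at 0.05. The section names no post hoc test, contrast, confidence interval or multiplicity adjustment.

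**The concern.** The F test and the conclusion answer different questions. The F test asks whether the six load means are all equal. The conclusion names one of them as highest. Rejecting equality is compatible with two, three or four loads sharing the top, and the plan contains no step from the rejection to a named load.

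The promised means and SDs will let a reader see how close the loads look. They do not show how precisely two loads have been separated within the same people, because that depends on the correlation between loads, which an SD per load does not carry.

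At stake is the certainty of the main result. A single intensity could be carried into later protocols as the one with the strongest DTF although its neighbours fit the data equally well. If the comparisons are left to be chosen later, the choice ranges from none to all 15 pairs unadjusted. The latter has a simulated familywise error of about 37% when no loads differ and there is no F-test gate.

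**Working it through.** **Inputs from the documents.** Effect size 0.2, alpha 0.05, power 0.80 and n = 54 (Sample size calculation); six loads, hence 6 × 5 / 2 = 15 pairs (Procedure).

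**Assumptions not in the documents.** Effect size read as Cohen's f (SD of the true load means divided by the within-load SD); one cohort; compound symmetry; correlation ρ between loads of 0, 0.5 or 0.7; the shape of the DTF curve. Accessory-muscle activity is not modelled.

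**1. The plan's own figure.** For a within-person F test, λ = f² × n × m / (1 − ρ), with m measurements.

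- m = 6, ρ = 0: λ = 0.04 × 54 × 6 = 12.96 on 5 and 265 df; power 0.795 (80% needs 55).
- m = 6, ρ = 0.5: λ = 12.96 / 0.5 = 25.92; power 0.986 (80% needs 28).
- m = 6, ρ = 0.7: λ = 12.96 / 0.3 = 43.2; power 0.9998.
- m = 2, ρ = 0.5: λ = 0.04 × 54 × 2 / 0.5 = 8.64 on 1 and 53 df; power 0.82 (80% needs 52).

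More than one set of inputs lands near 54, so the text does not settle which test the 80% describes. The inflation does follow: 54 × 1.2 = 64.8, so 65 per cohort and 130 in all.

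**2. Curves, all scaled to f = 0.2.** Tent peaking at 60% MIP (0, 1, 2, 3, 2, 1); straight rise (0 to 5); smooth peak at 60% MIP, −(x − 3)² for x = 0 to 5; one load above five equal ones. For the straight rise, the SD of 0 to 5 is √(35/12) = 1.708, so one step is 0.2 / 1.708 = 0.117 SD.

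**3. Calculations.**

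- Wrong pick: 400,000 simulated sets of load means, each with error variance (1 − ρ)/54; the share in which the highest sample mean is not the truly best load.
- Tied loads: 54 people × 6 loads simulated. After a significant F, a load is tied with the top if it lies within 2.246 × √(2 × MSE / 54) of it (Hsu's comparisons with the best). Half-width at ρ = 0: 2.246 × √(2/54) = 0.43 SD; at ρ = 0.5: 2.246 × √(1/54) = 0.31 SD.
- Paired power, best against next best, unadjusted: dz = gap / √(2(1 − ρ)), noncentral t on 53 df. Straight rise at ρ = 0.5: dz = 0.117 / 1 = 0.117, noncentrality 0.117 × √54 = 0.86, power 0.135.

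| Curve | Gap, best to next (SD) | Wrong pick, ρ = 0 / 0.5 / 0.7 | Mean DTF given up (SD), same order | At least one tied load after significant F, same order | Paired power, ρ = 0 / 0.5 |
|---|---|---|---|---|---|
| Tent | 0.21 | 23 / 11 / 4% | 0.051 / 0.023 / 0.009 | 95 / 89 / 76% | 0.19 / 0.33 |
| Straight rise | 0.12 | 32 / 21 / 14% | 0.049 / 0.028 / 0.017 | 97 / 94 / 90% | 0.09 / 0.135 |
| Smooth peak | 0.07 | 54 / 46 / 40% | 0.044 / 0.033 / 0.027 | 99 / 99 / 99% | 0.06 / 0.08 |
| One load higher | 0.54 | about 1% or less | about 0.006 or less (0.011 × 0.537) | 52 / 14 / 1% | 0.78 / 0.97 |

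**4. Reading.** For the three gradual curves, the gap to the next load is well inside the half-width at ρ = 0 and at ρ = 0.5. The F test can have power of 0.99 because it draws on the best-to-worst spread (about 0.6 SD), while neighbouring loads stay unresolved. The pick lies within one 10% step of the best load in 92% to 99% of studies at ρ = 0 and 97% to 99.9% at ρ = 0.5.

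**5. Sensitivity.** At ρ = 0, a smooth peak at 70% MIP and a saturating curve give 63% and 69% wrong picks; the tent at ρ = 0.9 gives 0.1%. The assumed shape and correlation drive the size.

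**The case against.** The strongest reply is that the Procedure describes a selection for later work, using two criteria. Taking the highest mean is a legitimate selection rule and does not require the winner to beat each neighbour. The second criterion may separate loads that tie on DTF: above 60% MIP, in healthy adults and ventilated patients, the Introduction reports that "the accessory respiratory muscle (in particular the sternocleidomastoid muscle) would be activated dramatically". Wrong picks cost little DTF, and every percentage above rests on assumed curves.

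Much of this stands. It limits the point to the DTF part of the rule and keeps it modest. It does not remove the gap, because the Aims and the Abstract are worded as identifying the strongest or most effective intensity. A tie-breaker can only be seen to work if the ties are reported, and the accessory-muscle criterion has no stated threshold.

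Three stronger readings are tempting and are not supported.

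- A reader might infer that 54 is too small or miscalculated. The effect tested, number of measurements, correlation and number of groups are not stated, so the figure can be neither confirmed nor called wrong.
- A reader might infer that the 80% is specifically power for a six-load comparison within one cohort. The text does not say so, and other inputs also give about 80%.
- A reader might infer that the study will name the wrong load about half the time. That holds for one assumed curve at low correlation; if one load alone stands out, the error nearly vanishes.

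**Conclusion.** The point holds as a gap in the statistical analysis, of minor to moderate weight. Followed as written, the plan can name one load as having the strongest DTF on the strength of a test that does not identify any load. The sizes in the table are illustrations conditional on f = 0.2, n = 54, six loads, compound symmetry and ρ from 0 to 0.7; the documents give no DTF means, SD or correlation to narrow them. What survives across the gradual curves is that neighbouring loads will usually remain unseparated even when the F test is significant. Because the pick is usually the best load or the one next to it, the damage is to the certainty of the claim and much less to the DTF achieved.

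**What to change.** - **Statistical analysis.** Add: for DTF in the stroke cohort (the cohort named in the aim), separately for the stroke and non-stroke side and with the side that defines the conclusion named in advance, within-person differences between loads will be estimated with multiplicity-adjusted simultaneous 95% confidence intervals. Fix one method beforehand, for example Bonferroni-adjusted paired differences, which do not need sphericity (Hsu's method with a pooled error term does). Report all loads not distinguishable from the highest mean. Analyse the healthy cohort the same way as secondary.
- **Abstract and Procedure.** Base the DTF part of the conclusion on that set. If one load is taken forward using the accessory-muscle criterion, report it with the set and its intervals. Which load is chosen stays with the investigators.
- **Sample size calculation.** Add only that the 80% refers to the repeated-measures ANOVA test and is not power to identify the best load.

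The cost is a few sentences, with no extra participants, visits or measurements. The real downside is that, for gradual curves, the DTF conclusion will often be several loads. Under the assumptions above, the mean set size with Bonferroni over 15 pairs is 4.9 to 5.1 of six loads at ρ = 0 and 3.9 to 4.6 at ρ = 0.5; with Hsu's method it is 3.8 to 4.4 and 2.9 to 3.9.

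### The DTF denominator rests on 3 resting images while each load yields 10 end-inspiratory readings; imaging 10 quiet expirations would cheaply reduce DTF error and could raise the test-retest ICC

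*Combined protocol and SAP*

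**What the plan says.** All references are to the combined protocol and SAP.

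- **Definition** (section 3, Introduction): DTF is given as "thickness of the diaphragm at end inspiratory - thickness at end expiratory)/thickness at end expiratory". End-expiratory thickness is therefore the denominator and also appears in the numerator.
- **Resting images** (section 4, Procedure): after 15 minutes of seated rest, both hemidiaphragms are imaged "at quiet breathing, the end of tidal inspiratory and the end of tidal expiratory, respectively", and "3 ultrasonic images will be captured to calculate the mean diaphragmatic thickness of each breathing status".
- **Loaded images** (section 4, Procedure): "Each MIP intensity protocol consists of 10 breaths", at six loads from 30% to 80% of MIP. Thickness of both sides "at the end inspiratory breaths of the 10 breaths of each MIP intensity protocol will be recorded". No end-expiratory image under load is described, and the text does not say how the 10 values become one.
- **Figure 1 legend**: the example images were taken "at the end of tidal expiration and the end of maximum inspiration at 30 %MIP", which fits a resting tidal denominator.
- **Second session** (section 4, Procedure): everything is repeated after 2 days "to examine the test-retest reliability of ultrasonographic measurements of DTF". Section 4, Statistical analysis, estimates this with an intraclass correlation coefficient. Neither the form of the ICC nor a target value is given.

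**The concern.** DTF can be written TEI/TEE − 1. An absolute error in TEI passes into DTF divided by TEE. The same error in TEE passes in divided by TEE and multiplied by TEI/TEE, which is 1.6 at a DTF of 60%. Replication runs the other way: up to 10 readings for each loaded TEI, 3 for the TEE that serves every load. Measuring six loads does not average the TEE error out, because it is the same at all of them within a session.

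The second session takes TEE afresh, so its error adds to the between-session difference at each load and lowers the ICC below what more images would give. That ICC is the stated purpose of the repeat visit, in at least 130 participants.

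The affected side may suffer more. The Introduction says that the affected diaphragm "was found only to have nearly 50% of those of healthy individuals". If image error is constant in millimetres, half the thickness means (1/0.5)² = 4 times the DTF error variance.

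**Working it through.** The plan states no figure on this point, so there is none to reproduce.

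**Inputs from the plan:** nE = 3 resting images; nI = 10 loaded readings; DTF = TEI/TEE − 1.

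**Assumed, because the plan gives none of them:** a typical DTF, the image error, the correlation between images, the between-person SD of DTF, and the day-to-day change.

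**1. Error variance with independent images and the 10 loaded readings averaged.** Write R = TEI/TEE.

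*Equal absolute SD at rest and under load:* Var(DTF) = (SD²/TEE²) × [1/nI + R²/nE]. At DTF 60%, R = 1.6 and R² = 2.56.
- nE = 3: 0.100 + 0.853 = 0.953; denominator share 0.853/0.953 = 90%.
- nE = 10: 0.100 + 0.256 = 0.356; reduction 1 − 0.356/0.953 = 63%.

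*Equal CV:* Var(DTF) = R² × CV² × [1/nI + 1/nE].
- nE = 3: 0.100 + 0.333 = 0.433; share 77% at any R.
- nE = 10: 0.200; reduction 54%.

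**2. Relaxing the assumptions.**
- *Noisier loaded images.* The share falls below half once the loaded CV exceeds √(10/3) = 1.83 times the resting CV. At 2 times it is 0.333/(0.333 + 0.400) = 45%.
- *One loaded value instead of a mean of 10.* Equal SD, R = 1.6: share 0.853/1.853 = 46%, reduction 1 − 1.256/1.853 = 32%. Equal CV: share 0.333/1.333 = 25%, reduction 1 − 1.1/1.333 = 17.5%.
- *Correlated images.* The variance of a mean is s² × [r + (1 − r)/n]. At r = 0.5 this is 0.667 s² for 3 images and 0.550 s² for 10. Equal CV: 1.217 falls to 1.100, a reduction of 10%. Equal SD, R = 1.6: 2.257 falls to 1.958, a reduction of 13%.

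**3. Effect on the ICC.** Two sessions were simulated for 200,000 people, with mean DTF 60%, between-person DTF SD 25 points, log-SD of TEE 0.2, independent images and averaged loaded readings.

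| Image SD | Session placement error | TEE 1.0 mm, 3 → 10 images | TEE 1.5 mm | TEE 2.0 mm |
|---|---|---|---|---|
| 0.2 mm | none | 0.57 → 0.79 | 0.76 → 0.90 | 0.85 → 0.94 |
| 0.2 mm | 0.1 mm on each thickness | 0.38 → 0.50 | 0.61 → 0.71 | 0.74 → 0.81 |
| 0.1 mm | 0.1 mm on each thickness | gain about 0.04 | gain about 0.03 | gain about 0.02 |

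An image SD of 0.2 mm is a per-image CV of 20%, 13% and 10% at the three thicknesses.

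*True day-to-day change.* ICC = between-person variance / (between-person + day-to-day + error variance). Take R = 1.5, between-person SD 0.25 (variance 0.0625), day-to-day SD 0.15 (variance 0.0225) and equal CV.
- CV 10%: error 2.25 × 0.01 × 0.433 = 0.00975, so ICC = 0.0625/0.09475 = 0.660. With 10 images, error 0.0045 and ICC = 0.0625/0.0895 = 0.698.
- CV 5%: 0.715 rises to 0.726.
- The denominator is then only 7.5% (CV 5%) or 23% (CV 10%) of between-session error.

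**4. Ranking of loads.** Within one side and session, all six TEI values are divided by the same TEE. The order of the six DTFs is the order of the six TEIs, whatever the error in TEE.

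**The case against.** A reader might infer that the denominator supplies most of the DTF error and that the number of resting images is what mainly limits reliability. The documents do not support either as fact. They need the 10 loaded readings to be averaged, images to be independent, and loaded CV to stay below about 1.83 times resting CV. The Procedure says only that the readings are recorded; a single value, such as the maximum, would also fit. Effortful breaths may well be harder to image than quiet ones, and repeated images at one probe position need not be independent. The repeat covers all procedures, which as written includes the MIP test, so the loads themselves may be reset between sessions; resting images cannot reduce that variation. This objection stands, and it is why the size is given as a range.

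A reader might also infer that the ICC would be biased or the choice of load compromised. Neither follows. The ICC would correctly describe the 3-image procedure, and no target is stated that it could miss. Sharing the denominator does not in itself alter the ICC at any one load, and the ranking of loads within a side and session cannot change.

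The fourfold penalty on the thin side is conditional as well. With constant CV there is none, and the Introduction does not say that its thickness comparison was made at end-expiration.

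Finally, the flow chart and figures are not in the text available, so it is likely rather than certain that the resting TEE is the only denominator.

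What survives is the imbalance in replication, its direction, and the low price of removing it. In every scenario calculated, 10 images gave less DTF error than 3.

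**Conclusion.** This is a cheap improvement, not an error in the plan. Three averaged images is a workable choice, but it puts the fewest replicates on the quantity to which DTF is most sensitive, in a study that repeats every procedure to measure DTF reliability.

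If the loaded readings are averaged and images are independent, matching the counts removes 54% (equal CV) to 63% (equal SD, DTF 60%) of image-related error variance. The reduction is 17.5% to 32% if one loaded value is used, and 10% to 13% if images correlate 0.5. The ICC gain is about 0.01 to 0.04 where placement error or true day-to-day change dominates. It is roughly 0.1 to 0.2 only where image error is large, for example 0.2 mm. The documents do not show which case applies.

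The claim does not extend to the study's main aim of finding the load with the strongest DTF, nor to any bias in the ICC.

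**What to change.** In section 4, Procedure:

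1. Capture end-expiratory thickness over 10 quiet breaths per side in each session, and name the mean of those 10 as the DTF denominator at every load. The other resting readings can stay at 3 images.
2. State that the 10 loaded end-inspiratory readings are averaged for each side and load. Without this rule the gain from the first change cannot be predicted.

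Cost: seven more quiet-breath images and caliper readings per side per session. Against the 6 × 10 = 60 loaded readings per side already planned, that is 7/60, or about 12% more. Imaging takes roughly half a minute, since both sides are scanned at once by the operators already present. No extra visits, staff or participants are needed.
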